3.14.3.10. Diabetic Retinopathy Complications

Any TEAE suspected of worsening retinopathy triggers a follow-up dilated fundoscopic exam. A summary of TEAEs suspected of worsening retinopathy and a summary of the results of the follow-up dilated fundoscopic exam will be summarized by treatment and PT. The cases with follow-up fundoscopy during the course of the trial, based on clinical suspicion of worsening retinopathy that have either findings of de novo retinopathy or progression of retinopathy, and severe/serious adverse events from PTs defined in searching criteria in Appendix 1 (Section 6.1) will be considered AESIs and summarized.

3.14.3.11. Renal Safety

3.14.3.11.1. *Acute Renal Events*

Laboratory measures related to renal safety will be analyzed as specified for laboratory measurements in Section 3.14.4. Two shift tables examining renal function will be created. A min-to-min shift table of estimated glomerular filtration rate estimated by the CKD-EPI equation with units ml/min/1.73m², using categories (less than 45, greater than or equal to 45 to less than 60, greater than or equal to 60 to less than 90, and greater than or equal to 90 ml/min/1.73m²). A max-to-max shift table of UACR, using the categories UACR less than 30 mg/g, greater than or equal to 30 mg/g and less than 300 mg/g, greater than 300 mg/g (respectively, these represent normal, microalbuminuria, and macroalbuminuria).

The AE database will be searched using SMQs of acute renal failure and chronic kidney disease to identify events consistent with acute renal events. The incidence of the resulting TEAEs will be summarized by treatment and PT. Detailed searching criteria can be found in Appendix 1 (Section 6.1). Severe/Serious acute renal events will be considered AESI.

3.14.3.11.2. *Dehydration*

The AE database will be searched using an SMQ of dehydration to identify events consistent with dehydration. Detailed searching criteria can be found in Appendix 1 (Section 6.1). Severe or serious dehydration events will be considered as AESIs.

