### **Other Medical Conditions**

36. Renal impairment measured as estimated glomerular filtration rate (eGFR) <30 mL/min/1.73 m^2, calculated by chronic kidney disease-epidemiology as determined by central laboratory during screening; for patients on metformin, eGFR <45 mL/min/1.73m^2 (or lower than the country-specific threshold for using the prescribed dose of metformin per local label)

- 37. Known clinically significant gastric emptying abnormality (for example, severe diabetic gastroparesis or gastric outlet obstruction) or chronically take drugs that directly affect gastrointestinal motility
- 38. History of chronic or acute pancreatitis. A patient with a history of acute pancreatitis caused by gallstones may be included in the study if the patient had a cholecystectomy to resolve the problem
- 39. Uncontrolled hypertension (systolic blood pressure ≥160 mm Hg and/or diastolic blood pressure ≥ 100 mm Hg). For participants with uncontrolled hypertension at the screening visit, antihypertensive medication may be started and blood pressure must meet the protocol criterion for hypertension control by the randomization visit
- 40. Uncontrolled inflammatory bowel disease (IBD) and/or not on stable therapy for the last 3 months or clinically symptomatic IBD with C-reactive protein >4 mg/L.
- 41. Any medical condition that, in the opinion of the investigator, may increase the risk of complications related to a liver biopsy (e.g., a known coagulopathy)
- 42. Any of the following cardiovascular conditions within 6 months prior to screening:
  - a. acute myocardial infarction (MI),
  - b. cerebrovascular accident (stroke),
  - c. unstable angina, or
  - d. hospitalization due to congestive heart failure (CHF)
- 43. New York Heart Association Functional Classification IV CHF
- 44. Have a serum calcitonin of
  - (a)  $\geq$ 20 ng/L at Visit 1 if eGFR is  $\geq$ 60 mL/min/1.73 m^2
  - (b)  $\geq$ 35 ng/L at Visit 1 if eGFR is  $\leq$ 60 mL/min/1.73 m^2
- 45. Have a known self or family history (first-degree relative) of multiple endocrine neoplasia type 2A or type 2B, thyroid C-cell hyperplasia, or medullary thyroid carcinoma (MTC)

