#### 8.3.7.13. Acute Renal Events

Renal safety will be assessed based on repeated renal functional assessment as well as assessment of AEs suggestive of acute or worsening of chronic renal failure. GI AEs may lead to dehydration, which could cause a deterioration in renal function, including acute renal failure. Patients should be advised to notify investigators in case of severe nausea, frequent vomiting, or symptoms of dehydration.

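### The renal shift table's lowest eGFR category is an open <45, so no planned table counts by arm the participants who fall below 30, the protocol's own exclusion threshold

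*SAP*

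**What the plan says.** SAP 3.14.3.11.1 (Acute Renal Events) specifies "A min-to-min shift table of estimated glomerular filtration rate estimated by the CKD-EPI equation", "using categories (less than 45, greater than or equal to 45 to less than 60", followed by 60 to <90 and ≥90. That makes four categories, the lowest open-ended. It is one of a pair of shift tables on kidney function. The other is a max-to-max table for UACR with categories <30, ≥30 to <300 and >300 mg/g.

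The entry rule is exclusion criterion 36 in Protocol 5.2. It excludes "Renal impairment measured as estimated glomerular filtration rate (eGFR) <30 mL/min/1.73" m² and, "for patients on metformin, eGFR <45 mL/min/1.73m"² or the country-specific limit for the prescribed metformin dose. A participant not on metformin may therefore be randomized with eGFR from 30 up to, but not including, 45.

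Protocol 8.3.7.13 explains why renal function is followed: "GI AEs may lead to dehydration, which could cause a deterioration in renal function, including acute renal failure". Acute renal events are on the list of adverse events of special interest in Protocol 8.3.7.

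The SAP has other renal outputs. The same section opens with "Laboratory measures related to renal safety will be analyzed as specified for laboratory measurements in Section 3.14.4", and it plans a search of the adverse event database for acute renal failure and chronic kidney disease.

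**The concern.** A shift table shows worsening only when a participant crosses into a lower category. With the floor at <45, two kinds of information are lost.

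- Participants who enter at 30 to <45 have no lower category to move to. In this table they read as unchanged however far they fall.
- Participants who enter at 45 or above can be seen to reach <45, but the table does not say whether they stopped at 40 or went below 30.

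The value of 30 is not an outside convention imported for the argument. It is the protocol's own renal exclusion limit. Protocol 7.1 also asks the investigator to call the sponsor when a participant develops an exclusion criterion during the study. An arm-level count of participants who reach that value is a natural safety summary for a drug whose gastrointestinal effects are named as a route to acute renal failure. The planned table cannot give it.

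**Working it through.** The plan states no figure that could be reproduced here. The check is to sort example pairs of lowest baseline and lowest postbaseline eGFR into the planned categories, and then into the same categories with extra cuts.

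**Inputs.** Planned cut points 45, 60 and 90 (SAP 3.14.3.11.1). Entry floor 30 for participants not on metformin, and 45 or the local limit for those on it (Protocol 5.2, criterion 36). The eGFR pairs are illustrations chosen to cover the cases; they are not trial data.

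**Rule.** A value's category is set by how many cut points it equals or exceeds. A shift is shown when the baseline and postbaseline categories differ.

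| Lowest baseline → lowest postbaseline | Planned cuts 45/60/90 | Cuts 30/45/60/90 | Cuts 15/30/45/60/90 |
|---|---|---|---|
| 40 → 35 | <45 to <45, no shift | 30–<45, no shift | 30–<45, no shift |
| 40 → 25 | <45 to <45, no shift | shift to <30 | shift to 15–<30 |
| 40 → 12 | <45 to <45, no shift | shift to <30 | shift to <15 |
| 31 → 14 | <45 to <45, no shift | shift to <30 | shift to <15 |
| 50 → 40 | shift to <45 | shift to 30–<45 | shift to 30–<45 |
| 50 → 25 | shift to <45 | shift to <30 | shift to 15–<30 |
| 50 → 12 | shift to <45 | shift to <30 | shift to <15 |
| 70 → 25 | shift to <45 | shift to <30 | shift to 15–<30 |
| 95 → 25 | shift to <45 | shift to <30 | shift to 15–<30 |

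**Results.**

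1. With the planned cuts, every pair with baseline below 45 reads as no shift.
2. With the planned cuts, 50 → 40, 50 → 25 and 50 → 12 fall in one cell. The fall shows; its depth does not.
3. One added cut at 30 makes 40 → 25, 40 → 12 and 31 → 14 visible and separates 50 → 40 from 50 → 25. It leaves 40 → 35 as no shift, which is reasonable.
4. A further cut at 15 only separates cases already below 30.

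**Do the other planned outputs supply the count?**

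- General laboratory shift table (SAP 3.14.4): the categories are low, normal, high and missing. A participant already low at baseline has nowhere lower to go.
- Descriptive statistics (SAP 3.2 and 3.14.4): the by-visit minimum gives one extreme value per arm and visit. It does not give the number of participants below 30 or their baselines.
- Abnormal-findings listing (SAP 3.14.4): this is by participant. A count could be made from it by hand, but it is not a by-arm table.
- Renal adverse event search (SAP 3.14.3.11.1): this counts reported events, not laboratory values below a threshold.
- Narratives (SAP 3.14.2): these describe individual participants with notable events.

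**Table size.** 196 / 4 = 49 randomized per arm. The planned table has 4 × 4 = 16 cells per arm, a cut at 30 gives 5 × 5 = 25, and cuts at 15 and 30 give 6 × 6 = 36.

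**The case against.** The strongest reply is that this is table layout and that a serious fall has several routes into the report. Creatinine is in the chemistry panel. Renal laboratory measures go through the general laboratory summaries. SAP 3.14 plans a repeated-measures model of change from baseline. Protocol 8.2.4 tells investigators to record clinically relevant laboratory changes as adverse events, and these feed the renal search. Serious events, discontinuations due to adverse events and severe events of special interest each get a narrative. Any shift table has a floor, and six categories for about 49 participants per arm would leave many cells empty. SAP 3.2 already allows additional analyses without amendment. All of this stands, and it keeps the point minor. It does not remove it, because none of these outputs is a by-arm count of participants below 30.

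A reader might infer more than the documents support:

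- **That falls below 30 are invisible.** They are hidden in this table only for a baseline of 30 to <45. From 45 or above the fall appears as a shift to <45, and other outputs may surface cases from either group.
- **That this is the main renal safety table, or the means by which acute renal events are found.** The SAP does not call it that. It identifies acute renal events through the adverse event search.
- **That a cut at 15 is needed.** Nothing in the documents anchors that value.

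**Conclusion.** The point holds as a minor, cheap improvement to reporting. For participants with baseline eGFR 30 to <45, the planned table cannot show any worsening. For those at 45 or above, it shows a fall below 30 without its depth. No planned table counts by arm the participants whose lowest eGFR goes below 30.

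The number affected cannot be computed. The documents give neither the distribution of baseline eGFR nor the share of participants on metformin, and the group entering at 30 to <45 may be small or empty. The conclusion rests on the wording of criterion 36 and of the category list. It does not depend on any assumed event rate, and it has no bearing on the efficacy analyses.

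The unassigned UACR value of exactly 300 mg/g is a drafting slip. It would not merit a point alone and is included because it sits in the same paragraph.

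**What to change.** In SAP 3.14.3.11.1, replace the <45 category with <30 and 30 to <45, keeping the other three. Alternatively, leave the table as it is and add one line per arm: the number and percentage of participants with lowest postbaseline eGFR <30. A further cut at 15 is optional. In the same paragraph, change the top UACR category from >300 to ≥300 mg/g.

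The cost is a short SAP edit and some sparse cells (25 per arm instead of 16 for the split table). The baseline <30 row should be empty or nearly so, because criterion 36 excludes those participants at screening. The single-line count avoids the sparse cells altogether. No new data are collected, and the change affects reporting only, not the management of participants.

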3.14.4. Clinical Laboratory Evaluation

All laboratory data will be reported in the International System of Units. Selected laboratory measures will also be reported using conventional units. Limits from the performing laboratory will be used to define low (L) and high (H). Descriptive summaries by treatment and by nominal visit will be provided for the baseline and postbaseline values as well as the change from baseline values.

Observed and change from baseline values for each visit may be displayed in plots for participants who have both a baseline and at least 1 postbaseline planned measurement. Baseline will be the last nonmissing observation prior to taking first study drug. Unplanned measurements will be excluded from plots.

A shift table will be provided including unplanned measurements. The shift table will include the number and percentage of participants within each baseline category (low, normal, high, or missing) versus each postbaseline category (low, normal, high, or missing) by treatment. The proportion of participants shifted will be compared between treatments using Fisher's exact test.

For qualitative laboratory analytes, the number and percentage of participants with normal and abnormal values will be summarized by treatment.

A listing of abnormal findings will be created for laboratory analyte measurements, including qualitative measures. The listing will include participant identification, treatment group, laboratory collection date, study day, analyte name, and analyte finding.

3.14.5. Immunogenicity

TE ADA are defined as those with a titer 2-fold (1 dilution) greater than the minimum required dilution (1:10) if no ADAs were detected at baseline (treatment-induced ADA) or those with a 4-fold (2 dilutions) increase in titer compared to baseline if ADAs were detected at baseline (treatment-boosted ADA). A patient is evaluable for TE ADA if the patient has a non-missing baseline ADA result, and at least 1 non-missing postbaseline ADA result.

The frequency and percentage of patients with preexisting ADA, with TE ADA, with neutralizing TE ADA, and with cross-reactive TE ADA to tirzepatide will be tabulated by dose, where proportions are relative to the number of patients who are TE ADA evaluable. The frequency and percentage of patients with hypersensitivity and injection site reactions by TE ADA status will be tabulated if warranted by the data.

A listing may be provided of all immunogenicity assessments for those patients who at any time had TE ADA present. This includes the tirzepatide concentration from a simultaneous PK sample, and the clinical interpretation result. A listing may be provided for all participants who had ADAs present at any time (including baseline) or had any hypersensitivity or injection site reaction TEAEs.

Depending on the number of patients with TE ADA, selected efficacy and safety subgroup analyses by TE ADA categories may be performed if deemed necessary. TE ADAs that are associated with AEs of either severe/serious hypersensitivity or severe/serious injection site reaction will be classified as AESI.

3.14.6. Vital Signs

Descriptive summaries by treatment and by nominal visit will be provided for baseline and postbaseline values as well as change from baseline values. If 2 records are taken at the same visit, they will be averaged prior to being used for data summaries and analyses.

An MMRM using REML will be used to fit the changes from baseline in vital signs at all scheduled postbaseline visits. The model will include baseline T2DM status (Yes/No), the region (Japan, US including Mexico, and Europe including Israel), treatment group, visit, and

treatment-by-visit interaction as fixed effects, and baseline value of the dependent variable as a covariate. To model the covariance structure within patients, the unstructured covariance matrix will be used.

Counts and percentages of patients with abnormal sitting systolic BP, sitting diastolic BP, and pulse will be presented by treatment. The criteria for identifying patients with treatment-emergent vital sign abnormalities are stated in [Table GPHR.3.3](#).

Table GPHR.3.3. Categorical Criteria for Abnormal Blood Pressure and Pulse Measurements

Parameter	Low	High
Systolic BP (mm Hg) (supine or sitting - forearm at heart level)	≤ 90 and decrease from baseline ≥ 20	≥ 130 and increase from baseline ≥ 20
Diastolic BP (mm Hg) (supine or sitting - forearm at heart level)	≤ 50 and decrease from baseline ≥ 10	≥ 90 and increase from baseline ≥ 10
Pulse (bpm) (supine or sitting)	< 50 and decrease from baseline ≥ 15	> 100 and increase from baseline ≥ 15

Abbreviation: BP = blood pressure.

3.15. Subgroup Analyses

Efficacy subgroup analyses will be guided by the efficacy estimand. Subgroups with few subjects may be excluded from subgroup analyses when appropriate. Subgroup analyses will include, but are not limited to:

- Primary and secondary endpoints by baseline T2DM status.
- Primary endpoint by baseline NAS score, using median NAS score to divide into 2 subgroups. In the case that baseline NAS score median is 4, NAS score 4, and NAS score greater than 4 will be the 2 subgroups.
- Primary endpoint by baseline liver fat (MRI-PDFF) category, using median to divide into 2 subgroups.
- Primary endpoint by baseline cT1 category, using median to divide into 2 subgroups.
- Primary endpoint by baseline serum NASH biomarkers (ALT, K-18, NIS4), using median (or cutoffs based on literature) to divide into 2 subgroups for each biomarker.
- Primary endpoint by categories of weight loss, using <5% and ≥5% as categories and then <10% and ≥10% as categories.
- Secondary endpoints of fibrosis regression and fibrosis progression by baseline fibrosis stage category (2 versus 3).
- Secondary endpoint of decreasing NAS by ≥2 points by baseline NAS.

- Secondary endpoints of fibrosis regression and fibrosis progression by baseline categories of serum fibrosis biomarkers (ELF and Pro-C3). For ELF, subgroups <9.8 and ≥ 9.8 (threshold for advanced fibrosis) will be analyzed (EASL 2021). For Pro-C3, subgroups <13.4 versus ≥ 13.4 and <20.2 versus ≥ 20.2 ng/ml (Nielsen et al. 2021) will be analyzed. If these subgroups for ELF and Pro-C3 are very imbalanced, the medians will be used to create the subgroups.

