# 9.2. Sample Size Determination

Approximately, 196 participants will be randomized to placebo, tirzepatide 5 mg, tirzepatide 10 mg, or tirzepatide 15 mg in a 1:1:1:1 ratio; assuming a 20% dropout rate, this results in approximately 40 completers per arm. Sample size selection is guided by the objective of establishing superiority of each tirzepatide dose to placebo relative to the proportion of participants achieving NASH resolution without worsening of fibrosis at 52 weeks from randomization. The evaluation of superiority to placebo will be conducted for each of the 3 tirzepatide doses at 2-sided significance level of 0.05 using a test of 2 proportions. The tirzepatide group mean response rate is assumed to be 42.5% and the placebo group mean response rate is assumed to be 12.5%. The chosen sample size provides at least 80% power to establish superiority of tirzepatide 5 mg, tirzepatide 10 mg, or tirzepatide 15 mg doses to placebo. No adjustment for multiplicity will be performed.

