### 9.4.7. Subgroup Analyses

Subgroup analyses of important factors, including fibrosis stage, amount of weight loss, baseline BMI, baseline liver fat content, T2DM status, and other factors to be specified in the SAP are planned for the key outcomes. The models used for these analyses will vary depending on the subgroups and the outcome. More details of the modeling will be provided in the SAP. Other exploratory subgroup analyses may be performed as deemed appropriate.

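### SAP 3.15 examines continuous and ordinal baseline markers as effect modifiers only through two-group splits; no treatment-by-marker model on the full scale is specified

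*SAP*

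**What the plan says.** SAP 3.15 (Subgroup Analyses) lists these modifiers for the primary endpoint:

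- Baseline NAS, split at its median. A grouping rule is given only for a median of 4.
- Liver fat: "Primary endpoint by baseline liver fat (MRI-PDFF) category, using median to divide into 2 subgroups".
- cT1: "Primary endpoint by baseline cT1 category, using median to divide into 2 subgroups".
- ALT, K-18 and NIS4: "using median (or cutoffs based on literature) to divide into 2 subgroups for each biomarker". The cut-offs are not named, nor is it said when they replace the median.

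For fibrosis regression and progression, ELF is cut at 9.8 and Pro-C3 at 13.4 and at 20.2 ng/ml, each with a citation. There is a fallback: "If these subgroups for ELF and Pro-C3 are very imbalanced, the medians will be used to create the subgroups". The SAP does not define very imbalanced.

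The section names no model, interaction term or interaction test. Protocol 9.4.7 had deferred this to the SAP (the quote breaks off just before that document is named): "The models used for these analyses will vary depending on the subgroups and the outcome. More details of the modeling will be provided in the".

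Three features of the plan limit the point. The SAP 3.15 list is stated not to be exhaustive. The endpoint of a NAS decrease of at least 2 points is examined by baseline NAS with no cut stated. And SAP 3.3, 3.11.2.1 and Table GPHR.3.2 enter the baseline value of several of these measures (liver fat, cT1, ALT, K-18, Pro-C3, ELF) as a covariate in that measure's own MMRM.

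**The concern.** A sample median has no clinical meaning and moves from trial to trial. A split there treats a participant just above the median like the one with the highest value, and as the opposite of the one just below. If response changes gradually with a marker, most of the evidence lies in the spread within each half, and the split discards it. A real gradient is then more likely to be missed, and the contrast that is reported depends on where this sample's median falls.

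The rules also leave choices open: which literature cut-off applies, what counts as very imbalanced, and which half a NAS of 5 joins if the median is 5. A full-scale model needs none of these choices.

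At stake is how well an exploratory Phase 2 trial describes who responds. The primary comparison is not affected. Nor are the subgroups that are binary by nature, such as T2DM status and fibrosis stage 2 versus 3.

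**Working it through.** **1. The plan's own sample size.** Protocol 9.2 compares the "doses at 2-sided significance level of 0.05 using a test of 2 proportions". It states: "The tirzepatide group mean response rate is assumed to be 42.5% and the placebo group mean response rate is assumed to be 12.5" per cent. It concludes: "The chosen sample size provides at least 80% power to establish superiority".

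- Evaluable: 196 × 0.8 = 156.8, or 39.2 per arm. Three doses pooled: 3 × 39.2 = 117.6, about 118.
- Size for 80% power: [1.96 × √(2 × 0.275 × 0.725) + 0.842 × √(0.425 × 0.575 + 0.125 × 0.875)]² / 0.30² = 33.6, so 34 per arm. With continuity correction it is 40.
- Fisher's exact power is 82.1% at 40 per arm and 80.8% at 39.

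The stated figure reproduces, but it covers the main effect only. The documents give no interaction size, no marker distribution and no subgroup power. Everything below therefore rests on assumptions.

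**2. Information kept by a median split.** A standard normal marker and its median-split version correlate at √(2/π) = 0.798, so the split keeps 2/π = 0.637 of the information on a linear gradient. If the full-scale test has non-centrality δ, the split test has 0.798δ, and power is Φ(δ − 1.96) + Φ(−δ − 1.96). For example, 50% power needs δ = 1.96. The split gives 0.798 × 1.96 = 1.564, and Φ(1.564 − 1.96) = 34.6%, a loss of 15.4 points.

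| Full-scale power | Median-split power | Loss (points) |
|---|---|---|
| 20% | 14.4% | 5.6 |
| 40% | 27.5% | 12.5 |
| 60% | 42.3% | 17.7 |
| 80% | 60.8% | 19.2 |

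**3. Simulation at the trial's size.** Marginal response was set to 42.5% and 12.5% with a standard normal marker. The test was a 1-df likelihood-ratio test of treatment by marker at two-sided 0.05, with 2,000 trials per scenario. The assumed log-odds slopes per SD are shown as drug / placebo. The interaction odds ratio is the exponential of their difference, for example e^(0.4 + 0.4) = 2.2.

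| Slopes | Interaction OR per SD | One dose, 39 vs 39: full / split | Pooled, 118 vs 39: full / split |
|---|---|---|---|
| +0.4 / −0.4 | 2.2 | 29% / 23% | 33% / 25% |
| +1.0 / 0 | 2.7 | 36% / 26% | 42% / 27% |
| +0.6 / −0.6 | 3.3 | 52% / 38% | 61% / 45% |
| +0.8 / −0.8 | 5.0 | 70% / 53% | 79% / 63% |

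With no interaction, rejection is 5.4% and 6.4% for one dose and 6.7% and 7.1% pooled (full, split). The comparison is fair, but all the powers are slightly high.

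**4. Sensitivity, at 40 vs 40 and 40 vs 120 pooled** (simulation error about 1 point).

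- Normal marker, gradient on drug only, OR 2 to 4: losses of 6.7 to 18.2 points for one dose and 8.2 to 21.0 pooled.
- Normal marker, OR 1.5: 12.6% vs 10.9% for one dose and 13.6% vs 11.4% pooled, about 2 points. With stratification terms in the model (assumed strata) the loss is about 1 point: 13.4% vs 12.6% and 12.4% vs 11.1%.
- Discrete NAS of 4 to 8 (assumed distribution), OR 2 to 4: about 5 to 15 points for one dose and 4 to 17 pooled.
- Right-skewed marker, linear on its raw scale, OR 2 to 4: about 11 to 29 points for one dose and 14 to 35 pooled. If the gradient is linear on a log scale that makes the marker normal, the normal case applies, because a median split is unchanged by taking logs.
- True effect a step at the median: splitting gains about 2 to 4 points (for example 37.6% vs 35.1%).

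Fixed cuts away from the median, and the fibrosis endpoints, for which the plan assumes no response rates, were not simulated.

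**5. Event counts.** Expected placebo responders are 39 × 0.125 = 4.9 in all, or about 20 × 0.125 = 2.5 per half.

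**The case against.** The strongest reply has four parts.

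*The loss belongs to a test the plan does not contain.* SAP 3.15 names no interaction test, so the power figures compare two analyses of which neither is specified. This stands. It also shows the underlying gap: the modelling detail that Protocol 9.4.7 deferred to the SAP is not there.

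*The effect sizes are chosen.* This stands too. An interaction odds ratio of 2 per SD is already large, and at 1.5 the loss is negligible.

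*The better analysis is already allowed.* The list is open, and SAP 3.2 permits additional analyses without amendment. True, but permission is not prespecification.

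*A full-scale model has its own weakness.* Its placebo slope rests on about 5 responders, with 3 or fewer in about 26% of trials. This stands, and the fix has to deal with it.

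A reader might also infer more than the documents support:

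- That these markers are never used on their full scale. Several are continuous prognostic covariates in their own MMRMs. What is missing is their full-scale use as effect modifiers.
- That the cuts are all unsupported. The ELF and Pro-C3 values are cited and come first; the median is only their fallback.
- That Phase 3 population choices depend on these analyses. The protocol names Phase 3 dose selection (Synopsis, 2.1) and the decision whether to continue to Phase 3 (4.2). It does not name population choice.

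**Conclusion.** The point holds as a cheap improvement to an exploratory analysis. For NAS, liver fat, cT1, ALT, K-18 and NIS4 on the primary endpoint, and ELF and Pro-C3 on the fibrosis endpoints, effect modification is examined only through two groups, and no full-scale treatment-by-marker model is specified.

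The size is conditional. A loss of about 6 to 18 points needs a roughly normal marker, a linear log-odds gradient, a median cut, the plan's primary-endpoint rates and an interaction odds ratio of about 2 to 5 per SD. It reached 21 points in one pooled scenario. It is about 0 to 2 points near 1.5 per SD, differs for discrete NAS, skewed markers and fixed cuts, and turns into a small gain under a step at the median. It should not be read as a known cost of this plan.

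The change makes these analyses more efficient but does not make them well powered. With the gradient on drug only and odds ratios of 2 to 4 per SD, full-scale power is about 23% to 53% for one dose and 26% to 64% pooled. SAP 3.6 calls the study exploratory and plans no multiplicity adjustment.

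**What to change.** In SAP 3.15, for each continuous or ordinal baseline marker, add the logistic model of Section 3.11.1.1 (with T2DM status and region) containing treatment, the marker on its own scale (log scale if skewed) and a treatment-by-marker term. Pool the tirzepatide doses first, then fit by dose. Use a small-sample method such as Firth's penalised likelihood, because only about 5 placebo responders are expected. Apply the same form to the fibrosis endpoints by ELF and Pro-C3, and to the NAS endpoint by baseline NAS.

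Report the interaction estimate with its 95% CI and the predicted treatment effect at the marker's 25th, 50th and 75th percentiles. Keep the two-group tables as descriptive display.

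The cost is SAP wording and one further model per marker and endpoint, on data already collected. The downside is the assumption of a linear log-odds gradient, which the retained tables help to check.
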